4.10.3 Secondary Efficacy Variables

The key secondary efficacy endpoints are change from baseline in VAS for pain score and the FACIT fatigue scale score to week 24. All efficacy analyses will be based on the ITT population and the double-blind period.

4.10.3.1 Key Secondary Endpoints

 Analysis of change in VAS for pain score from baseline to week 24 using ANCOVA (BOCF).

TP-GDO-WW-016-01 Confidential Version 7.0 Effective Date: 28Aug13 Version Date: 28NOV2018

Related to: SOP-GDO-WW-019 Page 24 of 60

• Analysis of change in FACIT fatigue scale score from baseline to week 24 using ANCOVA (BOCF).

The ANCOVA will include treatment group as fixed effect; the baseline measurements and stratification variables as covariates.

The missing data will be imputed by baseline observation carried forward (BOCF) method.

Additionally, sensitivity analyses using different imputation methods (random hot deck, imputation using OLE baseline/withdrawal visits) and MMRM using all collected data during the double-blind period will be performed as follows:

Random hot deck:

Random hot deck imputation method using a regression based approach will be conducted. In this imputation method, missing values will be replaced with values from a similar responding unit.

Imputation using OLE baseline/ withdrawal visits:

VAS for Pain and fatigue are assessed at OLE baseline visit for patients entering into OLE and the withdrawal visit for patients discontinuing from treatment. Missing values for patients that do not have a Week 24 assessment, but for which a pain /fatigue assessments is available between study days 85 and 252 from an OLE baseline or withdrawal visit, will be replaced with these values. The remaining missing values will be imputed using BOCF.

- Analysis of change in VAS for pain score from baseline to week 24 using ANCOVA by random hot deck imputation method.
- Analysis of change in FACIT fatigue scale score from baseline to week 24 using ANCOVA by random hot deck imputation method.
- Analysis of change in VAS for pain score from baseline to week 24 using ANCOVA with imputation using OLE baseline/ withdrawal visits
- Analysis of change in FACIT fatigue scale score from baseline to week 24 using ANCOVA with imputation using OLE baseline/ withdrawal visits

The following summary tables and analyses including all available visits in the double-blind period will also be provided as exploratory analyses:

- A summary table of change in VAS for pain score from baseline to every 24 weeks.
- A summary table of change in FACIT fatigue scale score from baseline to every 24 weeks.
- Analysis of change in VAS for pain score from baseline to every 24 weeks using MMRM analysis.

TP-GDO-WW-016-01 Confidential Version 7.0 Effective Date: 28Aug13 Version Date: 28NOV2018

Analysis of change in FACIT fatigue scale score from baseline to every 24 weeks using MMRM analysis.

The MMRM will include treatment group, protocol-specified visit, treatment-by-visit interaction as fixed effects; the baseline measurements and stratification variables as covariates: and visit as a repeated measure. The unstructured covariance matrix will be assumed in the model

If the unstructured covariance matrix does not converge, the length of the observation interval will be limited (e.g. to Week 96) and/or other covariance structure will be used. If treatment-by-visit interaction is not statistically significant, the full model will be kept.

If the normality assumption for the key secondary variable does not hold, GEE or Generalized Linear Mixed-effect model analysis will be used. The assessment will be performed prior to unblinding.

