3.2.5 Justification for Placebo-Controlled Trial

A placebo-controlled superiority trial comparing satralizumab monotherapy to placebo has been designed in this study. There are several key points to justify design of a placebo-controlled monotherapy study for approval of satralizumab:

- One of the primary rationales for a placebo-controlled study is the risk of mandating exposure of patients to unapproved drugs with safety profiles that are not well characterized based on results of randomized studies.
- Patients will be randomized in a 2:1 ratio to active treatment and placebo groups. This study design decreases the probability that on randomization a patient will receive placebo.
- The results of comparing satralizumab monotherapy to placebo would enable the evaluation of the safety and efficacy of satralizumab itself.

The need for placebo for scientific reasons:

A control treatment is generally considered necessary to demonstrate efficacy in various types of clinical trials, including NMO trials.

Placebo controls are needed to differentiate the pharmacologic and PD effects of a drug from the nondrug effects that patients experience in clinical trials. For example, the systematic attention by repeated examinations and frequent visits in a clinical study may lead to noteworthy placebo effects that patients are not exposed to in routine medical practice. Without a placebo group, these non-pharmacologic effects in the artificial environment of a clinical study cannot be distinguished from a real drug effect. Furthermore, many AEs seen in clinical trials are complaints that patients experience independent of drug therapy (e.g., headache, respiratory infections). Thus, the real safety and tolerability profile of a drug can best be evaluated by comparing the incidence of reported AEs with a placebo group.

Placebo controls offer a clear reference point, and they increase the likelihood of attaining statistical significance with a smaller sample size; this means that trials may be done more quickly and with a smaller number of patients.

Finally, the validity of the whole study as a measurement instrument can be proven by showing the difference of active drug versus placebo. If a study that has only active treatment arms does not show a difference between treatments, it cannot be known whether there actually was no treatment difference or if the study just failed to detect the difference (e.g., by poor design or conduct).

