6.2 DETERMINATION OF SAMPLE SIZE

Approximately 90 patients need to be recruited and randomized in a 2:1 ratio to the two treatment groups (satralizumab and placebo). The sample size considerations are based on the following assumptions:

- A two-sided log-rank test.
- At least 80% power at the 5% significance level.
- The hazard ratio of satralizumab over placebo for an initial 2 months from randomization is 1.0. The hazard ratio after an initial 2 months from randomization is 0.25.
- TFR in the placebo arm following an exponential distribution, with hazard rate for 1 year $h(t) = 1.1295$.
- A 2-year dropout rate of 10%.

Based on the assumptions, 44 TFR events are needed for the primary analysis. The 90 patients enrolled over 33 months and followed for an additional 5 months will provide 44 TFR events. The primary analysis will be performed once 44 TFR events have been observed or 1.5 years after the date of randomization of the last patient enrolled, whichever comes first. The Sponsor will conduct a blind review of the data including accumulation of events during the double-blind period and may take appropriate action such as to increase the number of patients or to extend the double-blind period based on this blind review.

It has been assumed that the number of relapses will follow a Gamma-Poisson distribution and that the variance/mean ratio will be a constant value of $\sqrt{2}$. This distribution was assumed and the ratio was estimated using data from MS trials (Gold et al. 2012; Kappos et al. 2010) because there are no approved medications for NMO and no raw data from patients with this indication are available.

Because the mean ARR of NMO patients is estimated at 0.82 and eligibility criterion 2 says patients at least 1 relapse in last 12 months prior to screening are selected, we calculate the zero-truncated mean of the Gamma-Poisson distribution with the mean of 0.82 and the mean and variance ratio of $\sqrt{2}$, then the baseline ARR is estimated at 1.65. The post-treatment ARR in the placebo group in NMO patients with anti-AQP4 positive and negative is estimated as 1.5 and 1.0, respectively (Cree et al. 2015). Given that the proportion of patients who are negative for anti-AQP4 antibody at screening will be capped at 30% of the total number of patients in this study, post-treatment ARR is estimated as 1.35.

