6.5.2 Secondary Efficacy Endpoints

Key Secondary Efficacy Endpoints

The key secondary efficacy endpoints are change in VAS for pain and change in FACIT fatigue scale. In order to control the rate of false positive conclusions, the serial gatekeeping methodology (fixed-sequence test) will be employed to control for multiple (primary and key secondary) endpoints in this order.

Change in VAS score for Pain

The VAS is a subjective measure of pain and it consists of a 100 mm line with two endpoints representing “no pain” and “pain as bad as it could be”. Patients are asked to rate their pain by placing a mark on the line corresponding to their current level of pain. The distance along the line from the ‘no pain’ marker is then measured with a ruler giving a pain score out of 10.

The change in VAS for pain score from baseline to Week 24 in the double-blind period will be analyzed by analysis of covariance (ANCOVA) method with baseline observation carried forward (BOCF) imputation. The analysis will include the categorical effects for treatment, prior therapy for prevention of NMO/NMOSD attack and the most recent attack in the last one year prior to screening, as well as the continuous covariates of baseline VAS for pain score.

Change in FACIT Fatigue Score

FACIT fatigue scale includes 13 questions, which measure fatigue/asthenia for patients with chronic, life-threatening illnesses. For each question, a patient rates his / her condition for the past week on a 5-point Likert scale ranging from 0 (not at all) to 4 (very much). For the change in FACIT fatigue, descriptive statistics will be calculated for the change in FACIT fatigue by averaging the individual question scores.

The change in FACIT fatigue Scale score from baseline to Week 24 in the double-blind period will be analyzed by ANCOVA method with BOCF imputation. The analysis will include the categorical effects for treatment, prior therapy for prevention of NMO/NMOSD attack and the most recent attack in the last one year prior to screening, as well as the continuous covariates of baseline FACIT fatigue score.

Further Secondary Efficacy Endpoints

Change in Short Form Generic Health Survey (SF-36) Score

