6.9 HANDLING MISSING DATA

For TFR, patients who have not relapsed at the time of analysis, the TFR will be censored on the date of end of the double-blind period (see the section “Length of Study” in PROTOCOL SYNOPSIS). Further details will be mentioned in the SAP.

For key secondary endpoints, missing data at Week 24 in the double-blind period will be imputed by a BOCF and for the purpose to assess the robustness of the imputation method, we will also conduct hot-deck imputation as sensitivity analysis.

For secondary continuous endpoints, a MMRM analysis incorporating data in double-blind phase will be used to utilize data collected over time with consideration of the variance-covariance matrix of the repeated measures. This method allows a general unstructured variance-covariance matrix and will include data from patients with incomplete data from some scheduled time points.

For the FACIT fatigue questionnaire, if there are less than 7 responses recorded, then the total fatigue score will be considered missing. If there are 7 or more responses recorded, then the total fatigue score for that questionnaire will be calculated as the average of the non-missing scores multiplied by 13.

Detailed methods for handling of missing data will be mentioned in the SAP.

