4.10.1.4 Multiple Comparisons/Multiplicity

The serial gatekeeping methodology will be employed to control the rate of false positive for the primary endpoint (TFR based on CEC confirmed protocol-defined relapses) and key secondary endpoints (change in VAS for pain to Week 24 and change in the FACIT fatigue scale to Week 24). The 3 efficacy endpoints will be analyzed in hierarchical order, beginning with the TFR based on protocol-defined relapses, followed by the VAS for pain, and ending with FACIT fatigue. A fixed-sequence approach will be applied to control the overall significance level at 0.05. An initial null hypothesis will be tested for the first hierarchical primary efficacy endpoint, the TFR based on protocol-defined relapses. If this is significant, then a repeat of the aforementioned testing procedure for the second hierarchical key secondary endpoint, the VAS for pain will be done. This will be repeated a third time for the FACIT fatigue if the VAS for pain showed a significant difference.

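### Should the two Week 24 key secondary tests rest on baseline carried forward, when relapse is the main expected cause of a missing score and is commoner on placebo?

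*SAP*

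**What the plan says.** The change from baseline to Week 24 in VAS pain and then in FACIT fatigue is tested after time to first relapse (TFR). SAP 4.10.1.4 states: "A fixed-sequence approach will be applied to control the overall significance level at 0.05". Protocol 6.5.2 says the VAS change "will be analyzed by analysis of covariance (ANCOVA) method with baseline observation carried forward (BOCF) imputation", with the same method for FACIT. Protocol 6.9 adds that "missing data at Week 24 in the double-blind period will be imputed by a BOCF", and SAP 4.10.3.1 agrees: "The missing data will be imputed by baseline observation carried forward (BOCF) method". SAP 4.10.3 sets the scope: "All efficacy analyses will be based on the ITT population and the double-blind period".

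SAP 4.10.3.1 also plans three alternatives for both endpoints: random hot deck, MMRM on double-blind data, and a method that fills a missing Week 24 score with one "available between study days 85 and 252 from an OLE baseline or withdrawal visit", leaving BOCF for the remainder. SAP 5.7 records that the last of these was added in Version 7.0.

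On relapse, Protocol 4.3.2.1 ends a patient's double-blind period at a CEC-adjudicated relapse. Protocol 4.3.2.2 lets extension dosing begin from Day 31 after onset. SAP 4.2 closes the efficacy window on the day before the first extension dose. In Protocol Appendix 1, VAS and FACIT are scheduled at Weeks 0, 24 and 48, then every 24 weeks, and again at extension Week 0 and the withdrawal visit. They are not collected at the extra visit for relapse.

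**The concern.** The drug is meant to prevent relapse, and relapse removes the Week 24 score, so missingness depends on treatment through the mechanism under test. BOCF gives every such patient exactly zero change. That withholds any improvement the patient had, and it also erases any worsening after the relapse, so it is not a consistent penalty for treatment failure.

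Suppose pain falls by the same amount in both arms for reasons unrelated to the drug. Protocol 3.2.5 says that "systematic attention by repeated examinations and frequent visits in a clinical study may lead to noteworthy placebo effects", and Protocol 4.4.1 allows pain medication to be started, or increased where control is insufficient. Placebo then loses more of that improvement than satralizumab, and BOCF alone produces a difference favouring the drug in a test that carries alpha. If instead relapse leaves lasting pain, BOCF hides part of a real benefit. In both cases the patient's own later score may exist and the confirmatory test does not use it.

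**Working it through.** **Inputs (Protocol 6.2, repeated in SAP 4.14).** Placebo hazard 1.1295 per year. The hazard ratio is 1.0 for two months; then: "The hazard ratio after an initial 2 months from randomization is 0.25". Allocation is 60 to 30. Dropout is 10% over two years.

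**The plan's own figure.** The placebo ARR is 0.7 × 1.5 + 0.3 × 1.0 = 1.35. With variance/mean ratio √2, the Gamma-Poisson zero probability is (√2)^(-1.35/(√2 - 1)) = 0.323, and -ln(0.323) gives a hazard of 1.1295 from the unrounded value. Both match the documents.

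**Scores lost to relapse.** For onset by day d, with t = d/365.25:
- placebo: 1 - exp(-1.1295 t)
- satralizumab: 1 - exp(-1.1295 × 2/12 - 0.25 × 1.1295 × (t - 2/12))

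| Score is lost if onset falls | Placebo | Satralizumab | Difference ΔL (unrounded inputs) |
|---|---|---|---|
| before Week 24 (d = 168) | 40.5% | 23.7% | 0.168 |
| by day 138 (Day 31 extension start) | 34.7% | 22.0% | 0.128 |
| by day 108 (60-day start, assumed) | 28.4% | 20.1% | 0.083 |

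The first row takes the double-blind period to end at the relapse itself. Under the SAP 4.2 window, the second row is the ceiling for patients who enter the extension. The third row needs a lag that neither document states. Dropout by Week 24 is only 1 - 0.9^(0.46/2) = 2.4% per arm.

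**Bias of BOCF.** Assume no direct drug effect on pain. Non-relapsers change by -m and relapsers by -m + r. Write R for the proportion relapsing by Week 24 and L for the proportion losing the score, with ΔR and ΔL as placebo minus satralizumab.
- Truth, satralizumab minus placebo: -r ΔR.
- BOCF: each arm's mean is -m(1 - L) + r(R - L), so the difference is -m ΔL - r(ΔR - ΔL).
- Bias = BOCF - truth = **-(m - r) ΔL**.

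With the Day 31 figure:
- m = 10 mm, r = 0: -10 × 0.128 = -1.3 mm, favouring satralizumab.
- m = r = 10 mm: 0.
- m = 0, r = 10 mm: +1.3 mm, against satralizumab.

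**Size against the noise.** No VAS SD is given. Assuming 22.5 mm, the standard error is 22.5 × √(1/30 + 1/60) = 5.0 mm, so 1.3 mm is about a quarter of it. The one-sided rate is then about Φ(-1.96 + 0.25) = 4.4% against 2.5%. Simulation with SD 20 to 25 mm, also requiring a significant TFR, gave 3.1 to 4.2% for this case.

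**Bias of the extension/withdrawal method.** With a Day 31 start, onset by day 54 puts the extension score before Day 85, so BOCF still applies. That is 1 - exp(-1.1295 × 54/365.25) = 15.4% in each arm. The two arms match because the hazard ratio is still 1.0, so this part cancels. The other lost patients contribute their own score. If that score is worse by f than it would have been at Week 24, the bias is **-f ΔL**.
- f = 0: no bias, where BOCF with m = 10 mm and r = 0 gives -1.3 mm.
- f = 10 mm, relapse effect gone by Week 24, m = 10 mm: -1.3 mm, the same as BOCF. Simulated one-sided rates were 4.7% (this method) and 3.9% (BOCF).
- f = 20 mm, otherwise the same: -2.6 mm against -1.3 mm. Simulated rates were 7.7% and 4.4%.

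**The case for a change.** The best argument for change is that the SAP already contains a method using the patient's own score, taken before the first open-label dose, and that promoting it needs no new data. The other two alternatives help little. A patient who leaves before Week 24 has no scheduled post-baseline double-blind VAS or FACIT score, so MMRM has nothing of theirs to use, and hot deck borrows from patients who did respond. A sensitivity analysis also does not carry the confirmatory test.

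Much of this stands. The lost proportions reproduce, they differ by arm, and no passage explains why BOCF suits missingness caused by relapse.

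The step from there to a correction does not stand. The inflated error rates need relapse to leave pain unchanged (r = 0), in a disease that Protocol 1.1.1 describes as marked by severe attacks and common pain. With r equal to m the bias is nil, and with r larger BOCF is conservative. The larger rates also assume a 20 mm common improvement, which nothing in the documents supports. No error rate was worked out for FACIT. The promoted method would bring subjective scores, usually recorded after rescue therapy and up to 12 weeks off schedule, into a test the SAP confines to the double-blind period. It improves matters only if the score at extension entry stands for the score at Week 24.

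**Conclusion.** BOCF is a real weakness here, but its bias has no known direction. On the planning hazards its size is 0.08 to 0.13 of (m - r), or up to 0.17 if every relapse before Week 24 loses the score. At an assumed 10 mm common improvement and no relapse effect, that is about 0.8 to 1.3 mm (1.7 mm at the extreme), against a standard error near 5 mm. The extension/withdrawal method removes this bias if the relapse effect is stable, matches it if a 10 mm effect has faded by Week 24, and doubles it if a 20 mm effect has faded. Choosing between them is a judgement about unknown quantities, so this is a fair trade-off.

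The useful alternative is already pre-specified for both endpoints and will sit beside the BOCF result. Protocol 1.3 reports the double-blind period as completed, so reassigning the confirmatory method now would be hard to defend. A count of BOCF-filled scores by arm and reason would help a reader, but it is ordinary reporting and alters no result. The primary TFR test is unaffected.

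These conclusions rest on planning hazards rather than observed relapse rates, and on assumed values for SD, m, r and f.

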4.10.3.2 Other Secondary Endpoints

The following summary tables, figures and analysis will be provided for the ITT:

- A summary table of change in SF-36 domain scores from baseline to every 24 weeks.
- A summary table of change in SF-36 summary score (physical and mental) from baseline to every 24 weeks.
- A summary table of change in EQ-5D scores from baseline to every 24 weeks.
- A summary table of change in T25W from baseline to every 24 weeks.
- A summary table of the proportion of relapse-free patients.
- A summary table of ARR.

The ARR is calculated as the total number of relapses experienced divided by the person-years at risk. The 95% CI will be presented based on the Poisson distribution. ARR based on the person-years at risk on the total study period will also be provided. In order to account for different study treatment exposure durations among subjects, log-transformed exposure time will be included in the model as an "offset" variable for appropriate computation of ARR.

- A summary table of ARR for patients with clinical relapse.
- A summary table of ARR for patients with treated clinical relapse.
- Analysis of ARR will be performed using negative binomial regression model (protocol-defined relapse).

For comparing the difference between 2 treatment arms, relapse number will be the response variable; treatment group, prior therapy for prevention of NMO/NMOSD attack (B-cell depleting therapy or immunosuppressants/others) and the most recent attack in the last one year prior to baseline (first attack or relapse) as covariates. Logtransformed exposure time will be included in the model as an "offset" variable.

A summary table of change in mRS scores from baseline to every 24 weeks.

TP-GDO-WW-016-01 Confidential Version 7.0 Effective Date: 28Aug13 Version Date: 28NOV2018 Related to: SOP-GDO-WW-019

- A summary table of change in ZBI scores from baseline to every 24 weeks.
- A summary table of change in EDSS scores from baseline to every 24 weeks.
- A summary table of change in visual acuity (Snellen chart) scores from baseline to every 24 weeks.
- A summary table of change in low-contrast visual acuity (Low-contrast Sloan letter chart [LCSLC]) scores from baseline to every 24 weeks.
- Analysis of change in SF-36 domain scores from baseline to every 24 weeks using MMRM analysis.
- Analysis of change in SF-36 components (physical and mental) from baseline to every 24 weeks using MMRM analysis.
- Analysis of change in EQ-5D scores from baseline to every 24 weeks using MMRM analysis.
- Analysis of change in T25W scores from baseline to every 24 weeks using MMRM analysis.
- Analysis of change in mRS scores from baseline to every 24 weeks using MMRM analysis.
- Analysis of change in ZBI scores from baseline to every 24 weeks using MMRM analysis.
- Analysis of change in EDSS scores from baseline to every 24 weeks using MMRM analysis.
- Analysis of change in visual function (Snellen chart) scores from baseline to every 24 weeks using MMRM analysis.
- Analysis of change in low-contrast visual acuity (Low-contrast Sloan letter chart [LCSLC]) scores from baseline to every 24 weeks using MMRM analysis.

The MMRM will include treatment group, protocol-specified visit, treatment-by-visit interaction as fixed effects; the baseline measurements and stratification factors as a covariate; and visit as a repeated measure. The unstructured covariance matrix will be assumed in the model.

If the unstructured covariance matrix does not converge, the length of the observation interval will be limited (e.g. to Week 96) and/or compound symmetric structure will be used. If treatment-by-visit interaction is not statistically significant, the full model will be kept.

If the normality assumption for other secondary variables does not hold, GEE or Generalized Linear Mixed-effect model analysis will be used. The assessment will be performed prior to unblinding.

